Program to Avoid Cerebrovascular Events through Systematic Electronic Tracking and Tailoring of an Eminent Risk-factor (PACESETTER)

	
PACESETTER intervention will comprise CCM components of delivery system redesign (home BP monitoring, increased follow-up visits, phone text messages), self-management support (patient education, dedicated phone texts), and community resources (guidelines, support groups, local information).	
Delivery system redesign (enhanced coordination of care) component of model strongly linked to improvements in health outcomes.⁶⁷⁻⁷⁰Self-management support (confidence in one's ability to behave in a way to produce a desirable outcome) component of model has been strongly linked to favorable outcomes.^{67,71,72}
--	---------------------------------------------------------------------------------------------------------------------------------------------------------------------------------------------------------------------------------------------------------------------------------------------------------------------------------------------------------------------------	-------------------------------------------------------------------------------------------------------------------------------------------------------------------------------------------------------------------------------------------------------------------------------------------------------------------------------------------------------------------------------------------------------

E.5. PACESETTER (Specific Aims 1-3)

- Aim 1: To conduct an implementation trial (at the patient level) of the PACESETTER intervention [health technology (personalized phone text messaging and home BP monitoring)] vs. usual care in 200 recent stroke patients with HTN recruited across two of the three main safety net hospitals in the state of SC. Primary outcome is achievement of guideline-recommended systolic BP control at 12 months.
- Aim 2: To explore whether implementation of the PACESETTER intervention vs. standard care is associated with a reduction in cardiovascular event-related emergency department encounters and re-hospitalizations within 12 months.
- Aim 3: To explore whether implementation of the PACESETTER intervention vs. usual care shows a signal of potential efficacy in reducing actual vascular events (stroke, myocardial infarction and death from vascular causes).

E.5.1. Eligibility

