Primary outcome is systolic BP at 12-months, which is the major modifiable step to stroke event rate reduction. A secondary analysis will examine whether PACESETTER improved systolic BP by a clinically significant amount. Also apart from the 12 month primary outcome, we will also conduct a longitudinal comparisons of systolic BP in IG vs. SC over the course of followup evaluations. Participants will be given an appointment encounter solely for collecting evaluation data at the times listed in Figure 2. Trained assessors blinded to the randomization arm (with no contact with PACESETTER clinical team and instructed not to infer and probe on the intervention) will perform all study measurements. Potential mediator/moderators of risk factor control will also be collected. If a patient endorses severe depressive symptoms, patient will be referred to the appropriate medical professional.

Table 3. PACESETTER Outcomes and Mediators

Outcome Type	Measurements	Assessment Duration	Target Goal	Baseline	4 months	8 months	12 months
Primary	Systolic blood pressure ^{173,174}	<15 mins	< 130 mmHg	X	X	X	X
Secondary	Cardiovascular ED encounters and re-hospitalizations	<10 mins	Group differences	X	X	X	X
	Medication adherence ¹²⁵	<10 mins	Group differences	X	X	X	X
	Body mass index ¹²⁶	<5 mins	Group differences	X	X	X	X
	Self-management ^{127,128}	<10 mins	Group differences	X	X	X	X
Tertiary	Stroke, Myocardial infarction, Death	<10 mins	Group differences	N/A	X	X	X
Mediators	Age, education, income, depression, ^{129,130}	<5 mins	Group differences	X	N/A	N/A	N/A
	HTN/stroke Knowledge, ^{131,132} Health literacy, ^{133,134} disability, ^{135,136} and study site	<10 mins	Group differences	X	X	X	X
	Side effects, Adverse events (as reported)	<10 mins	Group differences	X	X	X	X

E.5.5.1. Physiological/Laboratory Measures

i. BP measurements: Three readings will be taken by trained assessors (if patient is unable to be seen in person, trained assessor will confirm the readings are taken correctly by patient either by verbal confirmation of procedures or visually watching the patient complete the BP measurements) using an automated BP monitor with the patient seated comfortably for 5 min prior to the measurements, following guidelines.^{137,138} Average of the last two BP readings will be used as the measure for each visit. Uncontrolled BP is defined as average clinic systolic BP ≥ 130 mm Hg or diastolic BP ≥ 90 mmHg per guidelines.¹³⁷

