iv. Chart extraction: Information extracted from the medical records will include medications and their dosages, biomarker measurements from clinic visits, and medical comorbidities.

E.5.5.3. Vascular Events (Specific Aim 3)

PACESETTER aims to collect any vascular events that take place while a patient is in the trial. This is being done to ensure that all events are captured in a timely fashion without any recollection biases. In order to do this, all participants & families will be urged to contact the RC as soon as any event that might be a CVD event

Program to Avoid Cerebrovascular Events through Systematic Electronic Tracking and Tailoring of an Eminent Risk-factor (PACESETTER)

has occurred. CVD events will include stroke, transient ischemic attack, or an acute coronary syndrome. Participants with potential CVD events will be evaluated by a study physician within 48 hours. If the history or the exam indicates that a stroke might have taken place, all clinical, laboratory & imaging data needed to confirm the event will be obtained by the RC & sent to a blinded physician adjudicator assigned to each site (see letters of support), for independent review. Final reports regarding the event will be sent to primary research site (MUSC) within 15 days. Participants with events will continue to be followed at scheduled intervals. These are study-specific steps the patient or caregiver will be asked to take once the CVD event has been addressed medically- ie, after the condition been treated and stabilized.

E.5.6. Statistical Considerations

E.5.6.1. Randomization

Once eligibility, consent & baseline data are confirmed, participants will be randomly assigned to PACESETTER intervention vs. usual care in a 1:1 allocation ratio, stratified by race (Black and White) & study site. An adaptive block randomization scheme will be developed & maintained by the lead study biostatistician. Once a patient is randomized he or she will be entered into the study and included in intent-to-treat analysis. The randomization assignment will be known to the project coordinator, and the statistician in charge of the randomization procedure, but not known to the research assistant who will be conducting participant follow-up assessments.

E.5.6.2. Power and Sample Justification

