Descriptive statistics will be computed for all study variables, including average follow-up time, retention rate, protocol deviations and violations, and will be compared by treatment group. We will use t-test for continuous variables and chi-square test for categorical variables to make comparisons between two groups and corresponding ANOVA for more than two groups. The primary analysis will be performed according to the principle of intention to treat. All outcomes will be modeled using regression analyses adjusted for baseline factors that show imbalance after randomization and compared to analysis that does not adjust for residual baseline differences.^{140,141} A nominal p value of 0.05 or less will be considered as statistically significant in the primary analysis. Analysis of covariance (ANCOVA) will be used to test the hypotheses in Aim 2 adjusting for baseline differences. Assessment of the fit of the models will be made using residual and diagnostic plots. We will employ longitudinal data methods (generalized linear mixed models [GLMM]),¹⁴² which account for correlation of outcomes due to repeated measurements and clustering by site and missing at random (MAR) data to study the change in outcomes over time between the two groups. In addition, to evaluate sensitivity of study conclusions to missing data, we will use multiple imputation methods to estimate single end-point outcome measures and carry out analyses on the complete data set using the MNAR statement in SAS 9.4. If we suspect violation of MAR then we will do additional sensitivity analysis.¹⁴³ Trajectory or change over time in BP and other related outcomes will be modeled via GLMM. Differences in time to recurrent events between the two groups will be compared using a log-rank test and a Cox proportional hazards (PH) model (we will test for the PH assumption) will be used to adjust for observed confounders. Since all participant data will be included in this analysis, participants missing outcome data will be censored at the last follow-up assessment time. Exploratory analyses will also be performed by sub-groups (e.g. age, gender, race) to determine if any differential efficacy exists. If statistically significant differences are found between IG and CG arms, we will conduct regression analyses further adjusted by variables selected based on a combination of clinical judgment and descriptive statistical findings comparing

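### The exploratory Aim 3 vascular outcome is listed in three inconsistent ways, the time-to-event analysis names none of them, and blinded adjudication is written only for suspected stroke

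*Combined protocol and SAP*

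**What the plan says.** Four places in the combined protocol and SAP bear on the Aim 3 outcome.

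- **Section E.5, Aim 3** sets out to explore an early indication of benefit in "reducing actual vascular events (stroke, myocardial infarction and death from vascular causes").
- **Section E.5.5, Table 3** has a tertiary row reading "Stroke, Myocardial infarction, Death", collected at 4, 8 and 12 months. It does not limit the cause of death.
- **Section E.5.5.3**, whose heading names Specific Aim 3, opens broadly: "PACESETTER aims to collect any vascular events that take place while a patient is in the trial". It asks participants and families to report possible events promptly, then states "CVD events will include stroke, transient ischemic attack, or an acute coronary syndrome".
- **Section E.5.7.1 (Analysis)** says "Differences in time to recurrent events between the two groups will be compared using a log-rank test", with a Cox model for adjustment. It does not mention Aim 3 or define the event.

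On confirmation, section E.5.5.3 has two steps. First, "Participants with potential CVD events will be evaluated by a study physician within 48 hours". Second, "If the history or the exam indicates that a stroke might have taken place", the supporting records are gathered and "sent to a blinded physician adjudicator assigned to each site (see letters of support), for independent review". No other trigger for the second step is given.

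**The concern.** A time-to-event analysis needs one event definition, fixed before the data are seen. Here an analyst could follow any of three lists, or read recurrent events as recurrent stroke alone, and point to the plan for support each time. With few events expected in 200 patients, moving a handful in or out can change the p value materially.

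The adjudication rule also does not match the outcome it serves. Aim 3 counts MI and requires each death to be classed as vascular or not, but the only written route to a blinded reviewer is suspected stroke. Participants know their arm: one group has a pill tray, a connected blood pressure monitor and an app, and the other gets lifestyle messages. Event capture begins with participants or families contacting staff, and the plan does not say that the evaluating study physician is blinded. Blinded review therefore matters for the non-stroke components too.

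**Working it through.** **1. The lists side by side.**

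| Component | Aim 3 (E.5) | Table 3 | E.5.5.3 list |
|---|---|---|---|
| Stroke | yes | yes | yes |
| MI | yes | yes | yes, within acute coronary syndrome (ACS) |
| Other ACS | no | no | yes |
| TIA | no | no | yes |
| Vascular death | yes | yes | not listed |
| Other death | no | yes | not listed |
| Blinded adjudication trigger in E.5.5.3 | stroke only | stroke only | stroke; a suspected TIA may also qualify |

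Only stroke and MI are common to all three, and only stroke has a clear route to the adjudicator.

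**2. No figure to reproduce.** The documents give no event rate, hazard ratio, event target or power for Aim 3. Everything below rests on assumed rates and indicates size only.

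**3. Share of events counted under only one list (Aim 3 against E.5.5.3).** Assumed over 12 months in 200 patients: Aim 3 composite 5% to 10% (10 to 20 events), of which vascular death 1% to 3% (2 to 6); TIA or non-MI ACS 2% to 5% (4 to 10).

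Share = (vascular deaths + TIA/other ACS) / (Aim 3 composite + TIA/other ACS)

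- Low ends together: (2 + 4)/(10 + 4) = 6/14 = 43%
- High ends together: (6 + 10)/(20 + 10) = 16/30 = 53%

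The formula treats each event as a separate patient. In a first-event analysis, a patient who has a stroke and later dies is counted under both lists, so the true share would be lower. Table 3 is not part of this calculation.

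**4. Effect on the log-rank test.** A simulation used 100 patients per arm, 12 months, 20% dropout and 2,000 runs per scenario. Assumed 12-month control rates, low to high, were: stroke 4% to 8%, MI 1% to 3%, vascular death 1% to 3%, other death 1% to 3%, TIA 1% to 5%, non-MI ACS 0.5% to 2%. All three lists were applied to the same simulated patients.

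| No true effect | Low | Mid | High |
|---|---|---|---|
| Mean events, Aim 3 | 10.5 | 16.4 | 24.0 |
| Mean events, Table 3 | 12.2 | 19.0 | 29.0 |
| Mean events, E.5.5.3 | 11.3 | 20.4 | 29.7 |
| Median gap, largest minus smallest p | 0.27 | 0.29 | 0.32 |
| Chance that at least one list gives p < 0.05 | 7.8% | 9.0% | 10.2% |

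Any single list gave p < 0.05 in 3.8% to 5.4% of runs. With an assumed hazard ratio of 0.6, power was 9% to 23% across lists and scenarios. Schoenfeld's formula asks for 121 events for 80% power at that ratio.

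**5. Part of the Aim 3 composite with no written adjudication trigger**, from the same rates: low (1 + 1)/(4 + 1 + 1) = 33%; high (3 + 3)/(8 + 3 + 3) = 43%.

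**The case against.** The three texts do different jobs. Aim 3 states the outcome. Table 3 is a schedule with short labels, where death may be shorthand for vascular death. The E.5.5.3 list can be read as a reporting net, which may reasonably be wider than the endpoint; it is not worded as exhaustive, and the section opens by promising to collect any vascular event. Death is scheduled for collection in Table 3. On that reading the plan is ambiguous and one sentence would clear it up. This is fair, but the text does not settle it, and even as a reporting net the list omits death, which the other two places count.

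The link to the log-rank and Cox analysis is also not explicit. The only recurrent event named in the statistical sections is recurrent stroke, in E.5.6.2. If that is what E.5.7.1 means, stroke is in every list and has the adjudication route, so that analysis would not depend on the choice of list. This stands as a possible reading. It would, however, leave the Aim 3 composite without a stated time-to-event analysis.

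On review of events, a reader might infer that MI goes unreviewed or that vascular death cannot be assigned. Neither follows. A study physician evaluates every potential event, and the lack of a written procedure does not make classification impossible. Section E.5.5.2 also has a blinded statistician identify cardiovascular hospital encounters from state discharge codes. That serves the utilisation outcome, relies on coded diagnoses, and is not tied to Aim 3.

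Finally, Aim 3 is exploratory, its outcome is tertiary, and E.5.6.2 concedes that the sample is too small to detect a difference in recurrent stroke. This stands and limits the severity.

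**Conclusion.** The point holds as an inconsistency in an exploratory outcome, together with an adjudication rule that does not cover that outcome. The primary analysis of systolic blood pressure is untouched, so this should be corrected but does not threaten the trial's main result.

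Under assumed rates, roughly 43% to 53% of events counted under the Aim 3 or E.5.5.3 list would be counted under only one. This is on the high side because overlap within patients is ignored. Pairing opposite ends of the same assumptions would give (2 + 4)/(20 + 4) = 25% to (6 + 10)/(10 + 10) = 80%, but those pairings are mismatched; the upper one needs 6 of 10 composite events to be vascular deaths.

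A reader might also infer that the choice of list could reverse the direction of the treatment effect. That has not been shown: the simulation measured gaps between p values and the chance of a nominally significant result, not changes of sign. No choice of list would make the analysis decisive, given power of 9% to 23% at the assumed hazard ratio of 0.6.

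**What to change.** Fix one definition before any comparison by arm, and carry it through.

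- **Outcome.** Make time to first stroke, MI or vascular death, the set already stated in Aim 3, the single Aim 3 outcome in Table 3, E.5.5.3 and E.5.7.1.
- **Analysis (E.5.7.1).** Replace the reference to recurrent events with that outcome. State that non-vascular deaths are censored or, if preferred, treated as competing events.
- **Collection (E.5.5.3).** Label the existing list as a reporting net and add death to it.
- **Other events.** Report TIA, other ACS and all-cause death separately.
- **Adjudication (E.5.5.3).** Extend the trigger to any potential stroke, MI or death, including classification of cause of death, using the blinded adjudicators already assigned to each site.

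The cost is protocol wording and a handful of extra event packets for reviewers already in place. Sample size and the primary analysis do not change.

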morning and evening using the A&D device using a standardized resting BP protocol.^{40,41} BP readings were automatically sent via Bluetooth to the mobile phone and from there, through cellular network encrypted, to the secure and Health Insurance Portability and Accountability Act compliant data repository. No patient names were transmitted and no identifying information was stored on the smartphone. Participants received immediate audio and visual feedback via smartphone on average BPs after each measurement; and the application charted cumulative averages over time against threshold lines for BP control (i.e., set at <140/90 mmHg).⁷⁹ A weekly email report, tailored to the treating physician's guidelines, summarized the patient's adherence to medication dosing and BP monitoring, and BP data (i.e., average, range, % within recommended guideline classifications).⁷⁹ The treating physician made medical regimen changes as warranted, and the program coordinator was notified via email. The changes were duplicated in the programming of the medication tray after the coordinator established with the patient that the changes had been enacted. All patients received standard care (SC) at the hospital's stroke clinic, which included visits roughly every 6 weeks depending on the medical indication and time since index stroke. The mHealth group used the system for 3 months. Clinic BP readings and record of emergency department (ED) use were retrieved from patients' electronic medical records from the 6 months prior to the stroke, the 3 month period during the mHealth program, and the subsequent 3 months. Large reductions in clinic systolic BP were observed for mHealth group compared to the SC group (Figure 2). Mean systolic BP at baseline was 153.9 (standard deviation [SD]: 11.4) in the mHealth group vs. 156.7 (SD:26.5) in the SC group; at program end systolic BP was 136.3 (SD: 15.9) in the mHealth group vs. 151.3 (SD: 14.5) in the SC group; and 3 months post-program final systolic BP was 137.8 (SD: 24) in the mHealth group vs. 151.9 (SD: 13) in the SC group. Comparing the 6 month pre-stroke period vs. the 6 month period involving the QI program and followup, the mHealth group showed an 87.5% reduction vs. a 20% reduction in ED use by the SC group. Collectively, these data support the feasibility of using an mHealth medical regimen self management system to improve medication adherence and BP control after stroke.⁴²

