Our sample size calculation and power analyses are based on a 12 month change in the primary outcome of SBP, the premier modifiable risk factor for stroke. Large meta-analyses of observational and RCTs have found clinical benefit for having a SBP as low as 115 mm Hg. In addition, a large RCT of SBP-lowering for secondary stroke prevention found similar health benefits for persons with baseline HTN and for persons with baseline normotension. Data from MUSC clinic registry showed that the mean SBP for persons with SBP>120mmHg was 154.5 +/-10.3 mmHg. Using a type I error of 0.05, a power of 92%, a robust correlation of 0.8 between baseline and 12-months outcomes, no change in mean SBP in the control arm from baseline to 12 months and a two-sided test, 80 subjects in each treatment arm (or 160 subjects in total) will enable detection of a net decrease of 0.5 standard deviation units (which correspond to a difference of 8.8 mm Hg in SBP). This difference of 8.8 mm Hg in SBP between the two treatments is smaller than the 10 mm Hg threshold cited in the guideline, and thus we have sufficient statistical power with the estimated sample size to detect clinical benefit. An alternative outcome measure to SBP is recurrent stroke, but our sample size is not large enough to detect differences in recurrent stroke over 12-months of follow-up. Although we will facilitate the retention of subjects in the RCT as much as possible, the retention rates in disadvantaged populations are likely lower than in other settings. Assuming 20% loss to follow up, the conservative target for enrollment is 200. Data from MUSC indicated that 85% of all the patients at 3 days post-stroke had a SBP > 120. Thus, we conservatively expect ~50% will not meet eligibility criteria or may decline to participate, so we can potentially recruit over 200 patients including half of whom will be African Americans from the 2 sites over 3 years.

E.5.7. Data Management and Analysis

E.5.7.1. Analysis

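### The stated 92% power and 8.8 mmHg effect do not follow from the inputs in the power section, and the SD, the test and the use of baseline SBP are left open

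*Combined protocol and SAP*

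**What the plan says.** Section E.5.6.2 (Power and Sample Justification) opens with "Our sample size calculation and power analyses are based on a 12 month change in the primary outcome of SBP". Its inputs are "Using a type I error of 0.05", a two-sided test, "a power of 92%, a robust correlation of 0.8 between baseline and 12-months outcomes", no mean change in the control arm, and 80 evaluable patients per arm (160 in total). It concludes that this will "enable detection of a net decrease of 0.5 standard deviation units (which correspond to a difference of 8.8 mm Hg in SBP"). It then compares 8.8 mmHg with a 10 mmHg guideline threshold, judges power sufficient, and enrols 200 to allow for 20% loss.

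The only spread in the section is in this sentence: "Data from MUSC clinic registry showed that the mean SBP for persons with SBP>120mmHg was 154.5 +/-10.3 mmHg". It is not labelled as an SD or a standard error. No SD of change and no test or formula is given.

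Two other places bear on the calculation. Section E.5.5 states "Primary outcome is systolic BP at 12-months". On the model, section E.5.7.1 states "All outcomes will be modeled using regression analyses adjusted for baseline factors that show imbalance after randomization", to be compared with an analysis without that adjustment. It names ANCOVA only for Aim 2 and describes mixed models for change over time.

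**The concern.** A sample size statement should let a reader recover the power from the effect, the SD, the correlation, the test and the number per arm. Here the mmHg effect does not match the one spread shown, and the power matches no 12-month comparison that the section could be describing.

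The two gaps are separate. The first is the conversion from SD units to mmHg. The second is the power in SD units, which does not depend on the value of the SD.

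The role of baseline is also at stake. A baseline correlation of 0.8 raises power only if the analysis uses baseline SBP. If that is decided after looking for imbalance, the calculation relies on something the analysis may not do. The claim of adequate power against 10 mmHg depends on both the SD and this choice.

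**Working it through.** **Inputs.** From E.5.6.2: n = 80 per arm, two-sided alpha 0.05, effect 0.5 SD = 8.8 mmHg, correlation ρ = 0.8, stated power 92%, spread 10.3 mmHg (read as an SD, which is an assumption). From C.4: pilot SDs of SBP. The value ρ = 0.5 used below is not in the plan; it is my assumption for a weaker correlation.

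**1. Conversion to mmHg.**
- 0.5 × 10.3 = 5.15 mmHg, not 8.8.
- 8.8 / 0.5 = 17.6 mmHg, the SD that the statement implies.
- Reading 10.3 as a standard error does not help: (17.6 / 10.3)² ≈ 2.9, a registry of about three patients.

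**2. Power in SD units.** The standardised effect is 0.5 / f, where f is the analysis SD divided by the raw SD. Power is from the noncentral t with 80 per arm.

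| Analysis | f | 0.5 / f | Power | n per arm for 92% |
|---|---|---|---|---|
| 12-month SBP, baseline unused | 1 | 0.500 | 88.2% | 92 |
| Change score, ρ = 0.8 | √(2(1 − 0.8)) = 0.632 | 0.791 | 99.87% | 38 |
| ANCOVA, ρ = 0.8 | √(1 − 0.8²) = 0.600 | 0.833 | 99.95% | 34 |

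If 0.5 is in units of the SD of change, power is again 88.2%. A change SD of 17.6 would then imply a raw SD of 17.6 / 0.632 = 27.8.

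**3. What would give 92%.** With 80 per arm, 92% power needs a standardised effect of 0.535, so f = 0.5 / 0.535 = 0.934.
- ANCOVA: ρ = √(1 − 0.934²) = 0.36.
- Change score: ρ = 1 − 0.934² / 2 = 0.56.

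Neither is 0.8.

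**4. Size in mmHg.** The difference detectable with 92% power is 0.535 × f × SD. For ANCOVA at ρ = 0.5, f = √0.75 = 0.866.

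| SD (mmHg) | Detectable difference: unadjusted / ANCOVA 0.5 / ANCOVA 0.8 | Power for 8.8 mmHg, same order |
|---|---|---|
| 10.3 | 5.5 / 4.8 / 3.3 | all >99.9% |
| 15.0 | 8.0 / 7.0 / 4.8 | 96% / 99% / >99.9% |
| 17.3 | 9.3 / 8.0 / 5.6 | 89% / 96% / >99.9% |
| 17.6 | 9.4 / 8.2 / 5.7 | 88% / 95% / >99.9% |
| 22.8 | 12.2 / 10.6 / 7.3 | 68% / 80% / 98% |

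The SDs 22.8, 15.0 and 17.3 are pooled pilot values at baseline, program end and three months later. They assume that the 24 pilot patients split 8 and 16. For program end, C.4 gives "at program end systolic BP was 136.3 (SD: 15.9) in the mHealth group vs. 151.3 (SD: 14.5) in the SC group", so √((7 × 15.9² + 15 × 14.5²) / 22) = 15.0.

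The detectable difference reaches 10 mmHg at an SD of 10 / (0.535 × f): 18.7 unadjusted, 21.6 by ANCOVA at 0.5, and 31.1 by ANCOVA at 0.8.

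**5. Attrition.** 160 / 0.8 = 200, which reproduces.

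**The case against.** The strongest reply is that both figures have a plausible origin and that the error is harmless.

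- **The SD.** The six pilot SDs in C.4 (11.4, 26.5, 15.9, 14.5, 24, 13) have a simple mean of 17.55, and half of that rounds to 8.8. This may be the source. E.5.6.2 does not cite the pilot, however, and an unweighted mean of SDs across arms and times is not a declared planning value.
- **The power.** A visit-averaged repeated-measures formula with ρ = 0.8 between visits and no baseline term comes close. With f = √((1 + (m − 1)ρ) / m), power is 91.2% for m = 2 visits, 92.2% for 3 and 92.6% for 4. But this targets an average over visits, not the 12-month comparison named in E.5.5 and E.5.6.2. The two-visit version averages in the pre-treatment value. In this formula a higher correlation lowers power, the reverse of its effect in a change-score or ANCOVA test. A one-sided test gives 93.4%, but the plan says two-sided.
- **Use of baseline.** A 12-month change uses baseline by construction, and the mixed models in E.5.7.1 can do so too. That is fair, and ANCOVA is not the only option. The text still does not name the primary 12-month model.
- **Consequence.** With SD 17.6, ρ = 0.8 and baseline in the analysis, true power exceeds 92%, so the error is conservative. This stands. It does not hold for every SD in the plan: at 22.8 the detectable difference exceeds 10 mmHg both unadjusted and by ANCOVA at 0.5.

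The check covers continuous SBP only. Aim 1 words the primary outcome as achieving BP control, and neither the power paragraph nor this check addresses that binary form.

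**Conclusion.** The concern holds. The 8.8 mmHg is not half of the only spread in E.5.6.2. The 92% does not result from any two-sided 12-month comparison using the stated inputs, which give either 88% or more than 99%. The first conclusion assumes that 10.3 is an SD; the second holds whatever the SD is. Part of the document between C.4 and section E was not available for review, so an SD given there cannot be ruled out, but E.5.6.2 points to none.

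This is a defect in the justification, not evidence of too few patients. With 80 per arm, the 92%-power detectable difference stays below 10 mmHg up to an SD of 18.7 without baseline and up to 31.1 by ANCOVA at 0.8. It should be fixed because a reader cannot tell which SD, test or use of baseline the trial was sized for.

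**What to change.** Rewrite the power paragraph in E.5.6.2 so that it:

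- gives one SD with its source, for the eligible population (SBP of at least 130 rather than above 120), and says whether it is the SD of SBP or of change;
- names the test and says how the 0.8 enters it;
- restates power and detectable difference for that test. If SD 17.6 is meant, power for 8.8 mmHg with 80 per arm is 88% with no baseline adjustment, 95% by ANCOVA at a correlation of 0.5, and above 99.9% at 0.8. If SD 10.3 is meant, 0.5 SD should read 5.15 mmHg.

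Add one sentence to E.5.7.1 that prespecifies baseline SBP as a covariate in the primary 12-month SBP model, whether or not the arms look imbalanced.

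The cost is one paragraph, one sentence and one degree of freedom. Baseline SBP is already collected. The 200 enrolled, the visits and the endpoint do not change. The only option given up is deciding on the adjustment after seeing the data.
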